## 7.9.2 Secondary or other exploratory Efficacy analysis

### 7.9.2.1 Efficacy Analysis for paired comparison as Secondary analysis

For all the efficacy endpoint that treatment effect is significant in the Section 7.9.1.1 Primary Efficacy Analysis, the paired comparison of the placebo vs each active dose will be performed using the same model.

Point estimates and 95% CIs for the difference between each active dose and placebo will be generated as well.

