2.1.2 Secondary objectives

- To assess the dose-response effect and the minimum effective dose of MT-8554 on the frequency and severity of VMS.
- To assess the effect of MT-8554 on subjective sleep quality as measured by diary or insomnia questionnaires.
- To assess the safety and tolerability of MT-8554.

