4.1 Number of subjects

Approximately 364 subjects will be randomized in the study, with a target of 91 subjects in each treatment arm.

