7.5 Procedures for assigning subjects to treatment groups

Randomization will take place after confirmation of inclusion/exclusion criteria prior to dispensing the first study medication on Day 1. Subjects will be randomly allocated on a 1:1:1:1 basis to 1 of 4 treatments (Section 3.1). Subjects will be randomized with IVRS/IWRS system.

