10.3.5 Analysis of primary endpoints

Main Analysis

Change from baseline to Week 4 and Week 12 in the average daily frequency of moderate to severe VMS will be analyzed using a repeated measures analysis of covariance (ANCOVA) model with an unstructured covariance structure. The analysis model will include baseline value of the endpoint as a covariate; weeks, treatment, antidepressant using (Y,N), and interaction between antidepressant using (Y,N) and treatment as fixed effect. Relevant covariates will also be included in the model. If the normality assumption for the model is not met, a non-parametric method such as a ranked analysis of variance (ANOVA) will be performed.

The sensitivity analysis will be conducted using primary analysis model with applicable covariates for ITT subjects without using antidepressants.

Similar analyses will be conducted for VMS severity.

Comparison between each dose of MT-8554 and placebo will also be conducted using a repeated measures ANCOVA model. Point estimates and 95% CIs for the difference between each active dose and placebo will be obtained.

Further details will be provided in the SAP.

Secondary Analysis

The primary endpoints will also be analyzed using Maximum Contrast Methods with baseline value of the endpoint as a covariate, or slope approach¹³, as an analysis of the dose-response relationship. The detail will be specified in the SAP.

The primary endpoints will also be analyzed using an ANCOVA model.

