#### 5.2 Significance level and confidence interval

The statistical tests will be performed as two-sided with significance level of 5%. The confidence intervals will be determined with a confidence level of 95%.

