#### 7.9.1.1 Efficacy Analysis for Co-Primary Efficacy Endpoints

Change from baseline to Week 4 and Week 12 in the average daily frequency of moderate to severe VMS will be analyzed using repeated measures ANCOVA model with an unstructured covariance structure. The analysis model will include baseline value of the endpoint as a covariate and visits, treatment, interaction between visit and treatment, interaction between baseline and visit, antidepressant using (Y,N) , and interaction between antidepressant using (Y,N) and treatment as fixed effect. Baseline, weeks 1, 2, 3, 4, ..., 12 will be used for this analysis. (Table 14.2.1.1.A)

Similar analyses will be conducted for VMS severity score. (Table 14.2.1.2.A). The primary efficacy analysis will also be performed using PP population. (Table 14.2.1.1.B, Table 14.2.1.2.B)

If the normality assumption for the model is not met, the non-parametric method ranked ANOVA will be performed.

The scatter Plot of Mean change from baseline in VMS frequency and severity by treatment will be generated. (Figure 14.2.3.1, Figure 14.2.3.2). The scatter Plot of observed mean values of VMS frequency and severity by treatment will be generated. (Figure 14.2.4.1, Figure 14.2.4.2). The bar graph of Mean change from baseline in VMS frequency and severity at Weeks 4 and 12 by treatment will be generated. (Figure 14.2.5.1, Figure 14.2.5.2) The box plot of change from baseline in VMS frequency and severity by treatment will be generated as well. (Figure 14.2.6.1, Figure 14.2.6.2)

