### 7.12.4 Multiple Comparison/Multiplicity

In order to deal with multi-endpoint multiplicity, the efficacy analyses of primary and secondary endpoints will be conducted in the order fixed method. The details are described in Section 7.9 Efficacy Assessments.

The secondary analysis of primary variable and the analysis of other efficacy endpoints are performed from the exploratory perspectives and therefore no adjustment will be made for the multiplicity among variables and time points.

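### The SAP makes the dose-versus-placebo tests conditional on a significant overall treatment effect, an unlisted departure from the protocol, and sets no error control across doses once that condition is met

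*SAP*

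**What the plan says.** Protocol Section 10.3.5 states, under its main-analysis heading, "Comparison between each dose of MT-8554 and placebo will also be conducted using a repeated measures ANCOVA model". It then commits to point estimates and 95% CIs for each dose against placebo. Neither statement depends on another result.

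The primary model in SAP Section 7.9.1.1 is described as follows: "The analysis model will include baseline value of the endpoint as a covariate and visits, treatment, interaction between visit and treatment", plus further terms. It names no dose-specific primary contrast. SAP Section 7.9.2.1, which falls under the heading for secondary or exploratory analyses, then introduces the paired comparisons with "For all the efficacy endpoint that treatment effect is significant in the Section 7.9.1.1 Primary Efficacy Analysis". A separate sentence promises estimates and 95% CIs without saying whether the condition applies to them too.

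On multiplicity, SAP Section 7.12.4 orders the primary and secondary endpoints. It calls the secondary analysis of the primary variable exploratory and says "no adjustment will be made for the multiplicity among variables and time points". Doses are not mentioned. SAP Section 5.2 sets two-sided 5% tests and 95% CIs throughout.

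A stated secondary objective (Protocol Section 2.1.2) is "To assess the dose-response effect and the minimum effective dose of MT-8554 on the frequency and severity of VMS". SAP Section 8 lists two changes from the protocol: the antidepressant subgroup analysis is dropped, and so is the per-protocol analysis of secondary endpoints. The condition on the dose comparisons is not among them.

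**The concern.** Protocol Section 3.1 describes a dose-selection study, and the dose-versus-placebo comparisons are the most direct evidence for that purpose. The condition affects them in two ways.

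First, an overall test spreads its power over every pattern of difference among four arms. When the dose response is graded, it can miss while the comparison of the highest dose with placebo would succeed. Under the SAP that comparison would then not be run, although the protocol says it will be.

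Second, the overall test protects against false dose findings only when no dose works. Once one dose works well enough to satisfy the condition, the other doses are each tested at 5% with no joint control. That is the situation in which a minimum effective dose would be named.

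**Working it through.** **Inputs from the documents.** Two-sided 5% (SAP 5.2). Four arms allocated 1:1:1:1 (Protocol 7.5). For size, "Approximately 364 subjects will be randomized in the study, with a target of 91 subjects in each treatment arm" (Protocol 4.1); 4 × 91 = 364 agrees.

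**Inputs assumed.** The sample-size text is not in the public copy, so no power figure can be reproduced. I take a standardised 10 mg effect of d = 0.415, which gives 80% unadjusted pairwise power: SE = √(2/91) = 0.148, and 0.415/0.148 = 2.80 = 1.96 + 0.84. The check covers one endpoint at one time point, with known variance.

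**Power of the condition.** A four-level factor has 3 df (inferred; the SAP does not say so). The 5% critical value is 7.81 and the noncentrality is λ = n·d²·Σ(fᵢ − f̄)². Here fᵢ is each arm's effect as a fraction of d, with placebo = 0, and n·d² = 91 × 0.4153² = 15.70.

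- Only 10 mg works: Σ = 0.75, λ = 11.77, condition met 83%.
- 0.1, 0.5, 1: Σ = 0.62, λ = 9.73, met 75%.
- 1/3, 2/3, 1: Σ = 0.556, λ = 8.72, met 70%.
- 0.5, 0.75, 1: Σ = 0.547, λ = 8.58, met 69%.

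Simulation (1,000,000 sets of arm means) gives the joint results:

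| Effect at 1, 5, 10 mg | 10 mg significant, condition not met | 10 mg shown under SAP | 10 mg shown, ungated Dunnett |
|---|---|---|---|
| 0, 0, 1 | 5.7% | 74% | 67% |
| 0.1, 0.5, 1 | 10% | 70% | 67% |
| 1/3, 2/3, 1 | 13% | 67% | 67% |
| 0.5, 0.75, 1 | 14% | 66% | 67% |
| 0, 1, 1 | 2% | 78% | 67% |

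Ungated and unadjusted, 10 mg power is 80% in every row. With an F test and estimated variance the results are close: 79.7% falls to 73.8% if only 10 mg works, and to 65.6% for 0.5, 0.75, 1. If pairwise power were 90% instead, the losses would be 89.8 − 86.9 = 2.9 points and 89.8 − 80.1 = 9.7 points.

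**Error across doses once the condition is met.** Two null doses share the placebo arm, so their test statistics have correlation 0.5.

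- Either direction: 1 − P(|Z₁| < 1.96, |Z₂| < 1.96) = 9.07%. Independence would give 1 − 0.95² = 9.75%.
- Beneficial direction only: 1 − P(Z₁ < 1.96, Z₂ < 1.96) = 4.54%.
- With the condition applied at d = 0.415: 8.8% and 4.4%. Ungated Dunnett gives about 3.5% in either direction.
- All three doses null: the condition holds the either-direction figure to 4.0%. Without the condition and without adjustment it is about 12.5%.
- Only one null dose: 5.0% in either direction.

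**More than one result per dose.** With two results per dose, an assumed correlation of 0.3 to 0.8 and the condition met, the either-direction figure for two null doses is about 14–17% if either result counts and about 1–4% if both must be significant. The SAP does not say which rule makes a dose effective.

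**The case against.** The SAP places these comparisons among secondary and exploratory analyses in a Phase II trial, and leaving exploratory comparisons unadjusted is a declared and defensible choice. The type I error of the primary test is not affected. This stands, and it limits the point to the reliability of the dose-level evidence.

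A reader might infer that a null dose is called effective 9% of the time. The documents do not support that. The 9% counts differences in either direction over two null doses, and only when the third dose clearly works. In the beneficial direction it is about 4.5%, and 2.5% for one named null dose.

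A reader might also infer that a real 10 mg effect would disappear from the report. That goes too far. The sentence on estimates and CIs may be unconditional, and an unadjusted 95% CI gives the same answer as the unadjusted test. The exploratory contrasts in SAP Section 7.9.2.2 are not conditional either. In the graded scenarios, the linear contrast was significant in about 87–91% of the trials where 10 mg was significant but the condition failed. Those contrasts, however, are planned for frequency only, so severity has no such backup.

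Finally, it is tempting to say that Dunnett costs almost nothing against the SAP procedure. For the graded shapes the two are close, but elsewhere Dunnett loses 7 to 11 points, so relying on it alone is a real trade-off.

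**Conclusion.** The point holds in limited form. The protocol and SAP differ on whether the dose comparisons are always run, and Section 8 does not disclose it. That needs no calculation. The scope of the condition is also unclear: the SAP does not say whether it is the treatment effect over Weeks 1–12 or a test at each of Weeks 4 and 12, or whether it covers the CIs.

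The 10–14% and 6% figures rest on the assumed 80% pairwise power, on the effect shapes shown, and on one endpoint at one time point; they shrink if the true effect is larger. The 9% figure belongs to one configuration and should not be quoted as a general error rate. What is at stake is the evidence for dose selection and the minimum effective dose, not the validity of the primary test.

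**What to change.** 1. Delete the conditional clause in SAP Section 7.9.2.1. Always report the three dose-placebo differences with 95% CIs and p-values, for both co-primary endpoints at Weeks 4 and 12, as the protocol plans.
2. Show multiplicity-adjusted p-values beside the unadjusted ones. Deleting the condition alone would leave about a 12.5% chance of some false dose finding if no dose works.
3. Prespecify which adjusted procedure supports any minimum-effective-dose statement, and how the two endpoints and two time points combine. Dunnett is one option. A fixed sequence from the highest dose down, each step at two-sided 5%, is another: it keeps about 80% power for 10 mg with error across doses of at most 5%.
4. Mention doses explicitly in SAP Section 7.12.4, and record any remaining departure from the protocol in Section 8. If the condition is kept, define the test it refers to and state whether the CIs are exempt.

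**Cost.** SAP wording, an option in the LS-means step and slightly more output. If Dunnett governs the minimum-effective-dose statement, 10 mg power is about 7 points below the SAP procedure when only 10 mg works (74% against 67%) and about 11 points below when 5 and 10 mg work equally (78% against 67%). The fixed sequence avoids that loss but stops if the highest dose fails. This matters because contrast C4 in SAP Section 7.9.2.2 allows for a downturn at the high dose.

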### 7.9.2.2 Dose Response Analysis with Contrasts as exploratory analysis

The contrasts analyses will be performed for evaluating the dose effect. For change from baseline in the average daily frequency of moderate to severe VMS, the analyses with the following contrasts will be conducted. (Table 14.2.4) The corresponding 4 arms are placebo, MT-8554 1 mg, 5 mg, and 10 mg.

C1=(-3,-1,1,3) : dose response is linear

C2=(-5,-1,3,3) : dose response is reaching plateau at medium dose

C3=(-3,1,1,1) : dose response is reaching plateau at low dose

C4=(-1,0,1,0) : dose response goes downturn at high dose

C5=(-3,-3,1,5) : dose response is ineffective at low dose

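### SAP 7.9.2.2 lists five dose-response contrasts but no maximum statistic, joint reference distribution, model or week; read singly at two-sided 5%, they carry about a 12% chance of a false positive per time point

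*SAP*

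**What the plan says.** Protocol 10.3.5, under the secondary analysis of the primary endpoints, states: "The primary endpoints will also be analyzed using Maximum Contrast Methods with baseline value of the endpoint as a covariate". It offers a slope approach as the alternative and defers the detail to the SAP. Dose response and minimum effective dose, for both frequency and severity, form the first secondary objective (Protocol 2.1.2, SAP 1.1). Protocol 3.1 describes the study as one for dose selection.

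SAP 7.9.2.2, whose heading calls the analysis exploratory, states: "The contrasts analyses will be performed for evaluating the dose effect". It applies to the change in VMS frequency and lists five contrasts over placebo, 1, 5 and 10 mg, beginning with "C1=(-3,-1,1,3) : dose response is linear" and "C2=(-5,-1,3,3) : dose response is reaching plateau at medium dose". C3 is (-3,1,1,1), a plateau from the low dose. C4 is (-1,0,1,0), a downturn at the high dose. C5 is (-3,-3,1,5), no effect at the low dose. No model, week, combining rule or adjusted p-value is given.

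The only significance level available is the general one in SAP 5.2: "The statistical tests will be performed as two-sided with significance level of 5" per cent. SAP 7.12.4 treats the secondary analysis of the primary variable as exploratory and says "no adjustment will be made for the multiplicity among variables and time points"; it does not mention candidate shapes. SAP Section 8 lists two changes from the protocol, on the antidepressant subgroup and on the per-protocol analysis of secondary endpoints. It lists nothing on dose response.

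**The concern.** A maximum contrast test has two parts: a set of candidate shapes, and a single statistic (the largest contrast t) referred to the joint distribution of all of them. The SAP supplies the first part and not the second. A programmer following 7.9.2.2 literally would produce five unadjusted p-values, at whichever weeks were chosen, with nothing to say how they combine into a statement about dose response.

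The contrasts are highly correlated, so several can cross 0.05 together with no rule for reading them. At stake is how much weight a small p-value from this table can bear when a dose is chosen. The primary inference is not affected.

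**Working it through.** The visible documents state no error rate for the contrast family, so there is no planned figure to reproduce.

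**Inputs**

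- Level per test: two-sided 5% (SAP 5.2).
- Allocation: "Subjects will be randomly allocated on a 1:1:1:1 basis to 1 of 4 treatments" (Protocol 7.5).
- Size: "Approximately 364 subjects will be randomized in the study, with a target of 91 subjects in each treatment arm" (Protocol 4.1). With four arms, 364 - 4 = 360 residual degrees of freedom, as an approximation for one time point.
- Coefficients C1 to C5 (SAP 7.9.2.2).
- Assumption: no dose has any effect.

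**Correlations.** With equal arms, the correlation of contrasts a and b is sum(ab) / sqrt(sum(a²) × sum(b²)). The sums of squares are 20, 44, 12, 2 and 44 for C1 to C5. All five contrasts sum to zero.

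- Highest: C1 with C2, (15 + 1 + 3 + 9) / sqrt(20 × 44) = 28 / 29.66 = 0.944. C1 with C5 gives the same value.
- Lowest: C4 with C5, (3 + 0 + 1 + 0) / sqrt(2 × 44) = 4 / 9.38 = 0.426.

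**Joint null distribution.** Four independent arm means and a common variance estimate on 360 df were simulated 10 million times. All five t statistics were formed in each draw.

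| Quantity | Result |
|---|---|
| At least one two-sided p < 0.05 | 12.05% |
| Same, with mildly unequal arms | 11.8% to 12.0% |
| At least one significant in the benefit direction | 6.0% |
| Single two-sided 5% test, benefit direction | 2.5% |
| Five independent tests, 1 - 0.95^5 (upper reference only) | 22.6% |
| Critical value of the maximum absolute t for 5% overall | 2.35 (nominal p = 0.019) |

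The ratio in the benefit direction is 6.0 / 2.5 = 2.4. A smallest nominal p of 0.03 corresponds to about 0.075 once the maximum is allowed for. When any contrast is falsely significant, two or more are in about 55% of cases.

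**What the maximum can say about shape.** Doses 0, 1, 5 and 10 mg have mean 4, so a response linear in mg has centred coefficients (-4,-3,1,6), with sum of squares 62.

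- With C1: (12 + 3 + 1 + 18) / sqrt(62 × 20) = 34 / 35.21 = 0.966.
- With C5: (12 + 9 + 1 + 30) / sqrt(62 × 44) = 52 / 52.23 = 0.996.

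A response exactly proportional to dose therefore matches the shape labelled as ineffective at the low dose better than the shape labelled linear. C1 is linear in dose rank, not in mg.

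**The case against.** Four points tell against a stronger claim, and most of them stand.

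**Method.** A reader might infer that the SAP replaced the maximum contrast method with five separate tests. The documents do not say so. The protocol allowed an alternative and deferred the detail, and a list of candidate contrasts is exactly the input a maximum contrast test needs. The supportable reading is that the combining rule was left unstated.

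**Decision rule.** A reader might infer that a dose-response shape will be declared in 12% of null trials, or that a stated 5% error rate is more than doubled. SAP 7.9.2.2 never says that one p-value below 0.05 establishes dose response, and SAP 5.2 sets a level per test, not for a family. The 12% is conditional on reading each contrast at that level.

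**Status.** The SAP labels the analysis exploratory, and 7.12.4 claims no control for secondary analyses of the primary variable. Strict familywise control is therefore not owed. But 7.12.4 names variables and time points, not shapes, and the label does not tell a reader how to interpret the best of five correlated p-values.

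**Other evidence.** SAP 7.9.2.1 also provides placebo comparisons for each dose with 95% confidence intervals, after a significant treatment effect, so dose selection does not rest on the contrasts alone. If the contrasts were read only after a significant overall 3-df treatment test, the false-positive chance would be 3.7%. The SAP sets that gate for the paired comparisons and not for the contrasts.

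One further limit: the list of tables in SAP Section 11 is absent from the available text, so any note there on Table 14.2.4 could not be seen.

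**Conclusion.** The gap is real and modest in size. The method named in the protocol needs a maximum statistic and a joint reference distribution, and the SAP section meant to supply them gives neither, nor a model or a week. It also drops severity, which the protocol's plan and the objective both include, without listing that in Section 8.

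Read one by one at two-sided 5%, the five contrasts give about a 12% chance of at least one false positive per time point, and about 6% in the benefit direction against 2.5% for a single test. This assumes no dose effect, near-equal arms and approximately normal contrast estimates.

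Use at both Week 4 and Week 12 would raise the two-sided figure to about 16% to 21%. That rests on assumed between-week correlations of 0.9 to 0.5 and on a two-week use that the SAP does not specify, so it is an illustration and not part of the finding. The SAP should be changed here, because the contrasts serve a stated secondary objective in a dose-selection study and the remedy is the protocol's own method.

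**What to change.** In SAP 7.9.2.2:

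1. Define T as the largest absolute t over C1 to C5, estimated from the primary repeated-measures model with baseline as covariate.
2. Take its p-value from the joint multivariate-t distribution of the five contrasts, for example by simulation-based adjustment. With equal arms the 5% critical value is about 2.35.
3. Name the week at which the test is made. If more than one week is used, say that each is read separately under the waiver in 7.12.4.
4. Either apply the same test to severity or list its omission in Section 8.
5. Keep the exploratory label and show the individual contrast p-values as descriptive only.
6. Do not present the contrast that attains the maximum as an established shape, because the candidates correlate up to 0.94 and a response linear in mg fits C5 better than C1.

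The cost is SAP wording and one procedure option, with no change to design or data collection. The dose-response p-values become slightly less favourable: a nominal 0.019 is needed where 0.05 might otherwise have been read as enough.

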	
Secondary Analysis
 
The primary endpoints will also be analyzed using Maximum Contrast Methods with baseline value of the endpoint as a covariate, or slope approach, as an analysis of the dose-response relationship. The detail will be specified in the SAP.
 
The primary endpoints will also be analyzed using an ANCOVA model.
 
Secondary endpoints:
 
After the main analyses for all co-primary endpoints successfully show the treatment effect, efficacy analyses for the secondary endpoints may be continued in a fixed order as deemed appropriate as follows:
 
1. Proportion of responders at Weeks 4 and 12 (i.e., subjects with cutoff number* or greater reduction in the average daily frequency of moderate and severe VMS compared to baseline)2. Time to response, defined as time (in weeks) from randomization to the first time subjects meet responder criteria (i.e., cutoff number* or greater reduction from baseline in the average daily frequency of moderate and severe VMS)3. Change from baseline to Weeks 4 and 12 in the ISI total score 
The proportion of responders will be analyzed using a logistic regression model with treatment as fixed effect and baseline as covariate. The time to response will be analyzed with a log-rank test for each MT-8554 arm with placebo, with treatment as fixed effect and baseline as covariate. The VMS severity score and ISI will be analyzed using a procedure similar to the main analyses for co-primary endpoints.
 
Other efficacy endpoints:
 
Summary statistics will be presented for the change from baseline to Week 12 in Menopause-Specific QOL.
 
Other efficacy endpoints will be summarized by treatment groups using descriptive statistics.
 
Subgroup analysis:
 
The primary analysis model with applicable covariates will be conducted for ITT subjects who used antidepressants during the study. More subgroup analyses may be defined in the SAP.
 
Safety evaluation:
 
AEs are considered as treatment-emergent if they occurred after administration of the first dose of randomized study medication or if a pre-dose event increases in severity following dosing. The

--	---

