#### Secondary Objectives:

- To assess the dose-response effect and the minimum effective dose of MT-8554 on the frequency and severity of VMS.
- To assess the effect of MT-8554 on subjective sleep quality as measured by diary or insomnia questionnaires.
- To assess the safety and tolerability of MT-8554.

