### **3.4 Other Analysis**

There is no plan for analyses other than what is defined in this SAP.

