#### **7.9.1.2 Efficacy Analysis for the clinical response rate**

The clinical response rate will be analyzed using Logistic regression with treatment as fixed effects at Weeks 4 and 12. (Table 14.2.5)

The ROC curve will be created and cutoff number for responder will be calculated. (Figure 14.2.1)

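### The SAP runs the dose-response contrasts for VMS frequency only, although the protocol plans them for both co-primary endpoints, and SAP Section 8 does not record the change

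*SAP*

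**What the plan says.** Protocol 10.3.5, under its secondary analysis, says: "The primary endpoints will also be analyzed using Maximum Contrast Methods with baseline value of the endpoint as a covariate". It allows a slope approach as the alternative and leaves the detail to the SAP. The synopsis says the same: "The primary endpoints will also be analyzed using Maximum Contrast Methods with baseline value of the endpoint as a covariate, or slope approach". Protocol 2.2.1 defines two co-primary endpoints, VMS frequency and VMS severity.

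The secondary objective has the same wording in Protocol 2.1.2 and SAP 1.1: "To assess the dose-response effect and the minimum effective dose of MT-8554 on the frequency and severity of VMS".

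SAP 7.9.2.2 introduces the five contrasts C1 to C5 with: "For change from baseline in the average daily frequency of moderate to severe VMS, the analyses with the following contrasts will be conducted". It cites one table, 14.2.4, and does not mention severity.

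SAP 3.4 adds: "There is no plan for analyses other than what is defined in this SAP". SAP Section 8 lists two changes from the protocol: the antidepressant subgroup analysis is dropped, and the per-protocol analysis is not applied to secondary endpoints. Neither concerns dose response.

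**The concern.** This is a phase II study for dose selection, and dose response on both co-primary endpoints is a stated secondary objective. The protocol commits to a dose-response analysis of two endpoints and the SAP delivers it for one, without explanation. The severity half of the objective would then have no formal test for an ordered dose effect. A reader of the study report could not tell whether severity was left out by decision or by oversight.

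**Working it through.** **Step 1: set the texts side by side.**

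| Source | Endpoints covered by the dose-response analysis |
|---|---|
| Protocol 10.3.5 and synopsis | Primary endpoints (two) |
| Protocol 2.1.2 and SAP 1.1, secondary objective | Frequency and severity |
| SAP 7.9.2.2 | Frequency only |
| SAP Section 8 | No entry (0 of 2 listed changes) |

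**Step 2: could the frequency wording be shorthand for both endpoints?** Elsewhere the SAP says so when it means both, and it cites paired tables:
- SAP 7.9.1.1, main model: "Similar analyses will be conducted for VMS severity score", with Tables 14.2.1.1 and 14.2.1.2.
- SAP 7.9.4, analysis without antidepressant users: Tables 14.2.2.1 and 14.2.2.2.
- SAP 7.9.4, ANCOVA: names the primary endpoints, with Tables 14.2.3.1 and 14.2.3.2.
- SAP 7.12.5, subgroups: names the co-primary endpoints, with Tables 14.2.2.3.1 and 14.2.2.3.2.

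The contrasts have the single number 14.2.4, and 14.2.5 is already the responder analysis (SAP 7.9.1.2). The numbering therefore fits a frequency-only plan. The SAP's Section 11 table list was not in the text available for review, so this is strong evidence and not proof.

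**Step 3: how much detection is lost?** The contradiction needs no arithmetic. To give it a scale, compare the overall test of the four arms with the largest of the five contrasts.

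Inputs: 91 per arm (Protocol 4.1). The sample-size text is redacted, so the following are assumptions: effect f = 0.3, 0.45 or 0.6 SD at 10 mg; one time point; known SD; five dose-response shapes. The SAP does not say how the five contrasts are read together. With no effect, at least one of them passes 1.96 in 12% of trials, so a joint 5% critical value of about 2.34 is assumed.

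Formulas, with s the shape as a share of the 10 mg effect:
- Contrast statistic: T = Σcᵢȳᵢ / (SD·√(Σcᵢ²/91)), significant if the largest |T| exceeds about 2.34.
- Overall test: 3-df chi-square with noncentrality λ = 91·f²·Σ(sᵢ − s̄)².

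Example, effect proportional to mg: s = (0, 0.1, 0.5, 1), s̄ = 0.4, Σ(sᵢ − s̄)² = 0.16 + 0.09 + 0.01 + 0.36 = 0.62. At f = 0.3, λ = 91 × 0.09 × 0.62 = 5.08, which gives 44.8% power. At 0.45, λ = 11.43 and power is 82.0%. At 0.6, λ = 20.31 and power is 97.7%.

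Simulated results (400,000 draws per case), in % of trials at 0.3 / 0.45 / 0.6 SD:

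| Shape | Overall test significant | Largest contrast significant | Contrast significant, overall test not |
|---|---|---|---|
| Proportional to mg | 44.8 / 82.0 / 97.7 | 52.6 / 87.7 / 98.8 | 10.6 / 6.6 / 1.3 |
| None at 1 mg, half at 5 mg | 49.1 / 86.1 / 98.7 | 56.3 / 90.4 / 99.3 | 10.3 / 5.3 / 0.7 |
| log(dose + 1) | 43.7 / 81.0 / 97.4 | 54.6 / 88.3 / 98.9 | 12.4 / 7.8 / 1.5 |
| Emax, ED50 1 mg | 44.9 / 82.1 / 97.8 | 57.1 / 89.7 / 99.1 | 13.2 / 7.8 / 1.3 |
| Emax, ED50 2 mg | 44.7 / 82.1 / 97.7 | 56.4 / 89.5 / 99.1 | 12.9 / 7.7 / 1.4 |

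The last column is the relevant one: about 10-13 / 5-8 / 1%. The reverse case is rarer. For the proportional shape at 0.3 SD, the overall test alone is significant in 44.8 − (52.6 − 10.6) = 2.8%.

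**The case against.** The protocol leaves the detail to the SAP and offers a slope approach instead of contrasts, so the SAP may choose. That stands for the method. It does not settle which endpoints are covered, and the SAP gives severity no slope analysis either.

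The stronger objection is that severity is far from empty. A reader might infer that the trial would report almost nothing on how severity varies with dose. The SAP does not support that. Section 7.9.1.1 produces the severity model by arm and four sets of severity plots by treatment. Section 7.9.4 adds an ANCOVA at Weeks 4 and 12. Section 7.9.3 adds an ANCOVA of a related score weighted by frequency (Table 14.2.12). All of this is produced whatever the overall test shows.

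A reader might also infer that severity loses every dose-versus-placebo result when its overall test fails, because SAP 7.9.2.1 says: "For all the efficacy endpoint that treatment effect is significant in the Section 7.9.1.1 Primary Efficacy Analysis, the paired comparison" is performed. The condition sits in that sentence. The point estimates and 95% CIs come in a separate paragraph with no stated condition, and Protocol 10.3.5 gives them without one. The text is ambiguous at most. The rate at which the overall test fails (51-56 / 14-19 / 1-3% in the setting above) is therefore not a measure of this omission. It also depends on the single time point: for an effect averaged over 12 weeks, with assumed within-subject correlation of 0.5 to 0.8, it falls to about 22-48 / 1-11 / under 1%.

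Finally, the contrasts are labelled exploratory and SAP 7.12.4 makes no multiplicity adjustment among variables and time points for such analyses. This is correct and it limits the point. It does not explain why one endpoint was dropped.

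**Conclusion.** The inconsistency is real. The protocol plans the dose-response analysis for two endpoints, the SAP plans it for one, and Section 8 is silent. What is missing is the formal ordered dose-response contrast for severity, not dose information on severity in general. The primary tests, type I error and the primary conclusion are unaffected.

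The size is modest: a dose effect missed by the overall test but found by the contrasts in about 10-13 / 5-8 / 1% of trials at 0.3 / 0.45 / 0.6 SD. That range rests on the assumed effects and shapes, 91 per arm, one time point and a joint critical value that the SAP does not state. The contradiction itself rests on none of these. One reservation remains: the Section 11 table list could not be checked. If it contains a severity contrast table, the text of 7.9.2.2 would still need to match it.

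A reader might go further and conclude that the contrasts themselves are faulty. The documents do not support that. All five sets of coefficients are coherent with the order of the arms, and nothing in the SAP says that the largest contrast will be read as the true shape.

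**What to change.** Extend SAP 7.9.2.2 to the VMS severity score, using the same five contrasts with unchanged coefficients, reported in one more table paired with 14.2.4. If restricting the analysis to frequency was intended, say so in SAP Section 8 and give the reason.

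The cost is one more exploratory table and a second set of unadjusted exploratory contrasts, in line with SAP 7.12.4. A second set gives more chances of a false signal, so the results should be labelled exploratory like those for frequency. No data collection, primary model or significance level changes.
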